6.1.1.1 Treatment regimen

The recommended dose for the combination of LAG525 + spartalizumab and single agent dose of LAG525 have already been established ([CLAG525X2101C], Section 4.2) and will remain

constant at the established RDE (LAG525 400mg and spartalizumab 300mg both i.v. every 21 days).

Carboplatin will be dosed per AUC 6 given intravenously on day 1 of every 3-week cycle.

All drugs should be given on the same day.

Table 6-2 Dosing regimen

Dose Level	LAG525 (i.v.) mg	spartalizumab (i.v.) mg	carboplatin (i.v.)
Starting Dose	400mg Q3W	300mg Q3W	AUC 6 Q3W

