6.1.1.3 Carboplatin administration

Carboplatin will be administered every three weeks via i.v. infusion over 15 to 60 minutes once LAG525 and spartalizumab infusions are completed. A break of 30 minutes must be observed between any infusions. Any pre-medications should be administered as per local standard practice.

The dose of carboplatin will be adjusted in order to not exceed 900 mg corresponding to a GFR (based on the Calvert formula) capped at 125 mL/min FDA guidance 2010.

Doses subsequent to the initial dose administered at Cycle 1 Day 1 should be adjusted according to the local prescribing information for carboplatin.

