Study drug	Definition of last date of exposure of study drug	Example
------------	---	---------

LAG525 spartalizumab carboplatin	The planned end date of the last cycle in which the last non-zero dose of the investigational drug was last administered (i.e last date of administration + (planned interval duration-1day)) Note : If the subject died or was lost to follow-up before the derived last date, the last date of exposure to investigational drug is the date of death or the date of last contact, respectively. If the derived last date of exposure goes beyond the data cut-off date, it should be truncated to the date of data cut-off.	In a once every 3 weeks administration, the last date of exposure is the date of administration in the last cycle + 20 days
--	---	---

Summary of duration of exposure of LAG525, spartalizumab and carboplatin will include categorical summaries based on 21-day intervals (< 3 weeks, at least 3 weeks, at least 6 weeks, etc.) and using descriptive statistics (mean, standard deviation etc).

Cumulative dose

Cumulative dose of a study treatment is defined as the total dose given during the study treatment exposure and will be summarized for each of the study treatment components.

The **planned cumulative dose** for a study treatment component refers to the total planned dose as per the protocol up to the last date of investigational drug administration.

The **actual cumulative dose** refers to the total actual dose administered, over the duration for which the subject is on the study treatment as documented in the 'Study treatment – LAG525/PDR001/carboplatin' eCRF pages.

For subjects who did not take any drug component the cumulative dose for that component is by definition equal to zero.

For LAG525 and spartalizumab, the planned cumulative dose and actual cumulative dose will be expressed in mg.

For carboplatin, they will be expressed as calculated AUC (mg/mL x min). To that end the prescribed / administered dose in mg will be used to calculate the AUC using Calvert's formula based on the derived GFR value. Calvert's formula is given as:

- Carboplatin dosage (mg) = AUC (mg/mL x min) x [GFR (mL/min) + 25]

And the back-calculation for AUC is

- AUC (mg/mL x min) = Carboplatin dose (mg) / [GFR (mL/min) + 25]

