For the calculation of GFR, creatinine value in the database with a measurement time closest to the dosing date and the subject's age and weight at the creatinine collection time will be used with the Cockcroft & Gault formula. If the interval between the measurement time and dosing time is the same before and after dose, the measurement corresponding to the time before dose will be used. Cockcroft & Gault's formula ([Cockcroft and Gault 1976](#)) is given as:

- Male GFR (mL/min) = $[140 - \text{age (years)}] \times \text{weight (kg)} \times 1.23 / \text{sCr } (\mu\text{mol/L})$
- Female GFR (mL/min) = $[140 - \text{age (years)}] \times \text{weight (kg)} \times 1.04 / \text{sCr } (\mu\text{mol/L})$

OR

- Male GFR (mL/min) = $[140 - \text{age (years)}] \times \text{weight (kg)} / [72 \times \text{sCr (mg/dL)}]$
- Female GFR (mL/min) = $[140 - \text{age (years)}] \times \text{weight (kg)} \times 0.85 / [72 \times \text{sCr (mg/dL)}]$

Note: The planned dose of carboplatin is per AUC 6 in general, but could be lower if the corresponding dose (mg) was higher than 900 mg (maximum dose in mg allowed as per the protocol). Hence if for a subject the first carboplatin dose prescribed was capped at 900 mg, the prescribed carboplatin dose (AUC) will be back calculated and will be used as planned dose in AUC to compute the planned cumulative dose.

Dose intensity and relative dose intensity

Dose intensity (DI) for subjects with non-zero duration of exposure is defined as follows:

For LAG525 and spartalizumab, $\text{DI (mg / cycle)} = \text{Actual Cumulative dose (mg)} / \text{Duration of exposure to study treatment (cycle)}$,

For carboplatin, $\text{DI (AUC / cycle)} = \text{Actual Cumulative dose (AUC)} / \text{Duration of exposure to study treatment (cycle)}$,

where $\text{Duration of exposure to study treatment (cycle)} = \text{Duration of exposure to study treatment (day)} / 21$. It will be rounded up to the nearest cycle if the last date of exposure to study treatment is replaced by the cut-off date: e.g. 66 days will be rounded to 4 cycles.

If for example, the duration of exposure to spartalizumab is 6 weeks and the subject receives two injections of spartalizumab 300 mg:

$$\begin{aligned} \text{DI (mg/cycle)} &= \text{Actual Cumulative dose (mg)} / \text{Duration of exposure (cycle)} \\ &= 600 \text{ (mg)} / (42/21) \text{ (cycle)} = 300 \text{ (mg/cycle)} \end{aligned}$$

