For subjects who did not take any drug component the DI for that component is by definition equal to zero.

Planned dose intensity (PDI) is defined as follows:

For LAG525 and spartalizumab, $\text{PDI (mg / cycle)} = \text{Planned Cumulative dose (mg)} / \text{Duration of exposure (cycle)}$. PDI (mg / cycle) is 400 mg/cycle for LAG525 and 300 mg/cycle for spartalizumab.

For carboplatin, $\text{PDI (AUC / cycle)} = \text{Planned Cumulative dose (AUC)} / \text{Duration of exposure (cycle)}$.

Note: PDI (AUC / cycle) is AUC 6/cycle for carboplatin in general, but could be lower if the corresponding dose (mg) was higher than 900 mg. Hence if for a subject the first carboplatin dose prescribed is 900 mg, the prescribed carboplatin dose (AUC) will be back calculated and will be used as PDI per cycle for that subject.

Relative dose intensity (RDI) is defined as follows:

For LAG525 and spartalizumab, $RDI = DI \text{ (mg / cycle)} / PDI \text{ (mg / cycle)}$.

For carboplatin, $RDI = DI \text{ (AUC / cycle)} / PDI \text{ (AUC / cycle)}$.

DI and RDI will be summarized separately for each of the study treatment components, but using the duration of exposure of each of the components.

Some examples are given below on how to compute duration of exposure (cycle), planned/actual cumulative dose, PDI, DI and RDI in [Table 2-6](#) and [Table 2-7](#) for LAG525 and in [Table 2-8](#) and [Table 2-9](#) for carboplatin. For spartalizumab refer to LAG525 examples.

Table 2-4 Example 1 of LAG525 dose administration and exposure

Record number	Start/End Date	Dose Administered (mg)	Dose Stopped or Paused, Dose Interrupted?	Dose Permanently Discontinued	Reason
1	13Jun2018	400	No	No	
2	04Jul2018	400	No	No	
3	25Jul2018	400	No	No	
4	15Aug2018	0	Yes	No	AE

Duration of exposure (day) = (23Aug2018 = data cut-off date since LAG525 was not permanently discontinued) – (13Jun2018) + 1 = 72 days

Duration of exposure (cycle) for 72 days = 4 cycles (rounded from 3.4 cycles)

Planned cumulative dose (for 72 days, 4 cycles) = 1600 mg

Actual cumulative dose (for 72 days, 4 cycles) = 1200 mg

Dose intensity = (actual cumulative dose / duration of exposure in cycles) = 1200 mg / 4 cycles = 300 mg / cycle

Planned dose intensity = (planned cumulative dose / duration of exposure in cycle) = 1600 mg / 4 cycles = 400 mg / cycle

Relative dose intensity = $(DI / PDI) \times 100 = (300 \text{ mg/cycle}) / (400 \text{ mg/cycle}) \times 100 = 75\%$

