Planned cumulative dose (for 63 days, 3 cycles) = $5.9 \times 3 \text{ AUC} = 17.7 \text{ AUC}$, as dose prescribed is 900 mg, the planned dose is the planned dose prescribed (AUC)

Actual cumulative dose (for 63 days, 3 cycles) = 15.8 AUC

Dose intensity = (actual cumulative dose / duration of exposure in cycle) = $15.8 \text{ AUC} / 3 \text{ cycles} = 5.3 \text{ AUC} / \text{cycle}$

Planned dose intensity = (planned cumulative dose / duration of exposure in cycle) = $17.7 \text{ AUC} / 3 \text{ cycles} = 5.9 \text{ AUC} / \text{cycle}$

Relative dose intensity = $(\text{DI} / \text{PDI}) \times 100 = (15.8 \text{ AUC/cycle}) / (17.7 \text{ AUC/cycle}) \times 100 = 89.3\%$

Dose reductions or interruptions

The number of subjects who have dose reductions, administration stopped/paused during infusion or interruptions, and the reasons, will be summarized separately for each of the study treatment components.

‘Dose changed’, ‘Dose interrupted’, “Was drug administration stopped or paused” fields from the ‘Study treatment’ eCRF pages for each study treatment component will be used to determine the dose reductions, dose interruptions and administration stopped /paused, respectively.

The corresponding fields ‘Reason for change’ and ‘Reason for administration stopped or paused’ will be used to summarize the reasons.

A dose change is either ‘change in prescribed dose level’ or ‘dosing error’ where actual dose administered is different from the prescribed dose.

For the purpose of summarizing interruptions and reasons, in case multiple entries for interruption are entered on consecutive dose administrations with different reasons, separate interruptions will be counted. However, if the reason is the same in this mentioned multiple entries on consecutive dose administrations, then it will be counted as one interruption.

Reduction: A dose change where the prescribed dose level is lower than the previous prescribed dose level. Any dose change to correct a dosing error will not be considered a dose reduction. Only dose change is collected in the eCRF, number of reductions will be derived programmatically based on the change and the direction of the change.

Note: No dose reductions are permitted for LAG525 or spartalizumab.

For carboplatin, it is considered as a reduction only if the difference between the previous prescribed dose in AUC and the current prescribed dose in AUC is greater than 15% of the previous prescribed dose in AUC.

Notes:

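### When the first carboplatin dose is capped at 900 mg, its AUC becomes the plan for every cycle, so relative dose intensity can exceed 100% at the protocol dose once GFR falls

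*SAP*

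**What the plan says.** The dosing rule is in the protocol. Section 6.1.1.1: "Carboplatin will be dosed per AUC 6 given intravenously on day 1 of every 3-week cycle". Section 6.1.1.3: "The dose of carboplatin will be adjusted in order to not exceed 900 mg corresponding to a GFR" of 125 mL/min, with doses after Cycle 1 Day 1 adjusted according to local prescribing information.

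SAP 2.4.1 defines the exposure summaries:

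- Planned cumulative dose "refers to the total planned dose as per the protocol up to the last date of investigational drug administration".
- AUC is recovered from the milligram dose as mg/(GFR+25). GFR comes from the Cockcroft-Gault formula, using the "creatinine value in the database with a measurement time closest to the dosing date". No 125 mL/min ceiling is applied to this GFR.
- The planned dose is AUC 6, with one exception: "if for a subject the first carboplatin dose prescribed was capped at 900 mg, the prescribed carboplatin dose (AUC) will be back calculated" and used for planned cumulative dose. The same exception is repeated for PDI: "if for a subject the first carboplatin dose prescribed is 900 mg, the prescribed carboplatin dose (AUC) will be back calculated", and this first-dose AUC becomes the per-cycle value for that participant.
- The second carboplatin example (Table 2-7) applies the exception by multiplying the first-dose AUC of 5.9 by three cycles.
- A carboplatin reduction is counted only when the fall in prescribed AUC is "greater than 15% of the previous prescribed dose in AUC".

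RDI is DI divided by PDI. Protocol 12.3 plans it as a descriptive summary. The safety endpoint in protocol Table 2-1 is dose intensity.

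**The concern.** The numerator and denominator of RDI use GFR from different times. Delivered AUC follows the GFR at each dose, whereas the plan for a participant capped at the first dose stays at the first-dose GFR. The SAP lowers that plan below 6 because AUC 6 would have needed more than 900 mg. Once GFR falls, that reason weakens, and at 125 mL/min or below it no longer applies. The protocol target is then AUC 6 again. A participant never capped, with the same later GFR and the same later dose, is measured against 6.

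The result is a planned cumulative dose and PDI below the protocol plan. RDI reads above 100% at the protocol dose, and a real reduction is partly offset in RDI.

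**Working it through.** **The SAP's own figures.** Example 1 reproduces: (6+6+5)/18 = 94.4%. In Example 2 the fixed plan reproduces (5.9 × 3 = 17.7), but the stated RDI of 89.3% does not. The listed doses sum to 5.9+5.9+5 = 16.8, not 15.8, and 16.8/17.7 = 94.9%. This is a separate addition slip, and nothing below depends on it.

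**Inputs.** AUC 6 per cycle and the 900 mg limit come from protocol 6.1.1.1 and 6.1.1.3. The cap binds above GFR 125, since 6 × (125+25) = 900. AUC = mg/(GFR+25) comes from SAP 2.4.1. The documents give no GFR distribution, so the GFR values are assumptions. Six cycles without delay are also assumed.

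**Formulas.**

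- Protocol AUC at a dose = min(6, 900/(GFR+25)). GFR 150 gives 900/175 = 5.143; 140 gives 900/165 = 5.455; 130 gives 900/155 = 5.806; 127.5 gives 900/152.5 = 5.902; 125 or below gives 6.
- RDI under the SAP rule = sum of delivered AUC / (6 × first-dose AUC).
- RDI with a per-dose plan = sum of delivered AUC / sum of protocol AUC.

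| GFR in cycle 1, then cycles 2–6 | Later doses | Delivered | Fixed plan | Per-dose plan | RDI, SAP rule | RDI, per-dose plan |
|---|---|---|---|---|---|---|
| 127.5, then ≤125 | AUC 6 | 35.902 | 35.410 | 35.902 | 101.4% | 100% |
| 130, then 120 | AUC 6 | 35.806 | 34.839 | 35.806 | 102.8% | 100% |
| 140, then 115 | AUC 6 | 35.455 | 32.727 | 35.455 | 108.3% | 100% |
| 150, then 120 | AUC 6 | 35.143 | 30.857 | 35.143 | 113.9% | 100% |
| 130, then 120 | 900 mg held (AUC 6.207) | 36.841 | 34.839 | 35.806 | 105.7% | 102.9% |
| 150, then 120 | 900 mg held (AUC 6.207) | 36.177 | 30.857 | 35.143 | 117.2% | 102.9% |
| 150, then 120 | AUC 6 in cycle 2, AUC 5 in cycles 3–6 | 31.143 | 30.857 | 35.143 | 100.9% | 88.6% |
| 150, then 120 | AUC 5 from cycle 2 | 30.143 | 30.857 | 35.143 | 97.7% | 85.8% |

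**Does the reduction count catch it?** In the 100.9% row prescribed AUC goes 5.143, 6, 5. The step from 6 to 5 is 1/6 = 16.7%, above 15%, so it is counted. In the last row the step is (5.143−5)/5.143 = 2.8%, so the 15% rule does not count it, although the milligram dose falls from 900 to 5 × 145 = 725, or 19.4%. A direct step from a capped dose to AUC 5 exceeds 15% only if the previous AUC is above 5/0.85 = 5.882, that is, GFR below 900/5.882 − 25 = 128.

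**The SAP example under a per-dose plan.** The third dose, 750 mg at AUC 5, implies GFR 750/5 − 25 = 125 and a planned AUC of 6. The plan becomes 5.9+5.9+6 = 17.8, and RDI is 16.8/17.8 = 94.4% against 94.9%, a change of about half a point.

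**The case against.** **A first-dose plan is a disclosed convention.** The SAP states it twice and works an example. Protocol Table 6-2 labels AUC 6 a starting dose, and 6.1.1.3 refers later doses to local labels that are not in the documents, so a plan that moves with GFR is partly an interpretation. This is fair, but it does not settle the matter. Section 6.1.1.1 sets AUC 6 for every cycle, the SAP ties the planned dose to the protocol, and the SAP's own reason for departing from 6 is the cap. Applying that reason at each dose is the more consistent reading.

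**The listed endpoint is untouched.** A reader might infer that the dose-intensity endpoint is distorted. It is not: DI is actual cumulative dose over duration and never uses the plan. This objection stands in full.

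**Reductions are not hidden from the report.** A reader might infer from the 100.9% case that a reduction disappears. It does not: the step from 6 to 5 is counted, and the dose listings show each dose with reasons. Only a direct step from a capped dose may escape the count. Even that is arguable, because a note in the same section also counts decreases from the protocol starting dose. In that case delivered AUC itself falls only 2.8%; the shortfall is against the target of 6.

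**The remedy reaches further than the problem.** With GFR 120 then 150 for five capped cycles, the SAP gives (6+5×5.143)/36 = 88.1%, while a per-dose plan gives 100%. This stands as a consequence to be stated. It does not defeat the change, because the lower exposure remains visible in absolute DI. Nor does it add creatinine noise: above GFR 125 the ratio at a dose reduces to mg/900, and below it the planned AUC is simply 6.

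**Little now depends on it.** By amendment 4, 85 of 88 participants had stopped treatment, and SAP section 1 says no inferential analysis is planned for the close-out report. This bears on priority.

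**Conclusion.** The point holds as a minor one. For a participant whose first dose was capped and whose GFR later falls, the SAP's planned cumulative dose and PDI lie below the protocol plan, and RDI exceeds 100% at the protocol dose if there are no delays. Delays lower RDI and can hide the excess. The direction follows from the SAP's definitions; the size depends on assumed GFRs. It is about 1 percentage point for a first GFR near 127.5, 3 to 14 points in the other re-dosed cases above, and about 12 points of offset when AUC 5 is given in cycles 3–6 or from cycle 2 (100.9% against 88.6%; 97.7% against 85.8%).

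Only the descriptive carboplatin planned cumulative dose, PDI and RDI in Arms 2 and 3 are affected. Actual cumulative dose, DI, ORR and the efficacy rule are not. The documents do not say how many participants had a capped first dose or a later fall in GFR, so nothing supports a claim about arm-level bias.

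**What to change.** In SAP 2.4.1, define planned carboplatin AUC at each planned dose as min(6, 900/(GFR+25)), with the same GFR used for that dose's delivered AUC. For an omitted dose, use the GFR nearest the planned date. Sum these for planned cumulative dose, divide by cycles for PDI, and derive RDI from that. Rework the second carboplatin example to match and correct its sum (16.8/17.8 = 94.4%).

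State in the SAP that RDI will also be 100% at the full 900 mg for participants who first reach the cap after cycle 1, and that their lower exposure should be read from absolute DI. The change does not remove RDI variation from milligram doses held below the cap or from a site GFR that differs from the SAP-derived value, and it leaves the 15% reduction count as it is.

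The cost is SAP wording and a small programming change. GFR at each administered dose is already derived, and no new data are needed. If the primary CSR used the present rule, add a comparability note, because RDI may differ between the two reports for the same participants.

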2.1.1 General definitions

Investigational drug and study treatment

Investigational drug will refer to LAG525 or spartalizumab (PDR001), combination partner will refer to carboplatin only, whereas study treatment will refer to LAG525 + spartalizumab, LAG525 + spartalizumab + carboplatin or LAG525 + carboplatin.

The term investigational treatment may also be referred to as *study treatment* which is used throughout this document.

Date of first administration of investigational drug / combination partner

The date of first administration of investigational drug / combination partner is defined as the first date when a non-zero dose of investigational drug / combination partner is administered and recorded on the ‘Study treatment – LAG525/PDR001/carboplatin’ eCRF pages. The date of first administration of study drug / combination partner will also be referred as start of investigational drug / combination partner.

Date of last administration of investigational drug / combination partner

The date of last administration of investigational drug / combination partner is defined as the last date when a nonzero dose of investigational drug / combination partner is administered and recorded on the ‘Study treatment – LAG525/PDR001/carboplatin’ eCRF pages. The date of last administration of investigational drug / combination partner will also be referred as end of investigational drug / combination partner.

Date of first administration of study treatment

The date of first administration of study treatment is derived as the first date when a nonzero dose of study treatment was administered as per the ‘Study treatment – LAG525/PDR001/carboplatin’ eCRF pages. The date of first administration of study treatment will also be referred as *start of study treatment*.

The date of first administration of study treatment is derived as the first date when a nonzero dose of any component of study treatment was administered as per the ‘Study treatment – LAG525/PDR001/carboplatin’ eCRF pages. (Example: if 1st dose of spartalizumab is administered on 05-Jan-2018, and 1st dose of LAG525 is administered on 03-Jan-2018, then the date of first administration of study treatment is on 03-Jan-2018).

Date of last administration of study treatment

The date of last administration of study treatment is defined as the last date when a nonzero dose of study treatment was administered as per ‘Study treatment – LAG525/PDR001/carboplatin’ eCRF pages.

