- A prescribed dose reduction lower than the previous prescribed dose, but where the administered dose is 0 mg or higher than the prescribed dose, will not be counted as a dose reduction: see records 10 and 11 in [Table 2-10](#).
- A decrease in dose from the protocol planned starting dose or a decrease from the previous non-zero dose will be counted as a dose reduction even if this decrease has been directly preceded by an interruption: see record 8 in [Table 2-10](#).

- If the dose decrease is followed by an interruption, with the dose resuming at the same level prior to the interruption, the second dose decrease or change in dosing frequency will not be counted as dose reduction: see record 6 in [Table 2-10](#).
- If, due to a dosing error, a subject receives higher than protocol planned starting dose and moves down to the planned starting dose then this is not a dose reduction: see record 3 in [Table 2-10](#). However if the change is directly from a higher than planned starting dose down to a lower than protocol planned starting dose, then this is a dose reduction.
- If, due to a dosing error, a subject receives lower than previous non-zero dose and resumes later at the protocol specified dose reduction, then lower dose received due to dosing error and protocol specified dose reduction are dose reductions.
- If, due to a dosing error, a subject receives lower than previous non-zero dose and resumes later at lower than previous non-zero dose, then 2 dose reductions will be counted.

Table 2-8 Examples of possible dose changes for carboplatin and dose reduction outcome

Record number	Prescribed dose (AUC)	Administered dose (AUC)	Counted as a dose reduction (Yes/No)	Comment
1	6	6	No	
2	6.5	6.5	No	Dose increased by error
3	6	6	No	Correcting dosing error
4	5	5	Yes	Prescribed dose reduction (e.g. due to AE)
5	0	0	No	Dose interruption
6	5	5	No	Resume previous dose
7	0	0	No	Dose interruption
8	5	4	No	Dosing error (not a prescribed dose reduction)
9	5	5	No	Correcting dosing error in row 8
10	4	0	No	Prescribed dose reduction (e.g. due to AE) but not administered due to dosing error
11	4	5	No	Prescribed dose reduction (e.g. due to AE) but not administered due to dosing error
12	4	4	Yes	Prescribed dose reduction (e.g. due to AE) and row 11 was not counted as a dose reduction (administered dose was 5 by error)

Treatment beyond RECIST progression

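### The worked examples for dose intensity and dose reductions in SAP 2.4.1 do not follow that section's own rules, and one contains an addition error

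*SAP*

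**What the plan says.** **End of exposure.** For each drug, SAP Table 2-3 sets the last exposure date at the last non-zero dose plus 20 days on the three-weekly schedule. Death or loss to follow-up can bring it forward. The only rule on the cut-off is: "If the derived last date of exposure goes beyond the data cut-off date, it should be truncated to the date of data cut-off". Permanent discontinuation is not a condition. Days are divided by 21 to give cycles, and the result is "rounded up to the nearest cycle if the last date of exposure to study treatment is replaced by the cut-off date".

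**Planned cumulative dose** is "the total planned dose as per the protocol up to the last date of investigational drug administration". SAP 2.1.1 has the date of last administration "defined as the last date when a nonzero dose of investigational drug / combination partner is administered".

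**LAG525 Example 1 (Table 2-4).** Doses of 400 mg are given on 13Jun2018, 04Jul2018 and 25Jul2018, then 0 mg on 15Aug2018 for an adverse event, without permanent discontinuation. The example ends exposure on 23Aug2018, the "data cut-off date since LAG525 was not permanently discontinued". It prints 72 days, 4 cycles, 1600 mg planned and RDI 75%. LAG525 Example 2 (Table 2-5) has the same non-zero doses but is flagged as permanently discontinued. It prints 63 days, 3 cycles and RDI 100%.

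**Carboplatin Example 2 (Table 2-7).** The administered doses are 5.9, 5.9 and 5 AUC. The text prints "Actual cumulative dose (for 63 days, 3 cycles) = 15.8 AUC", dose intensity (DI) 5.3 AUC/cycle and RDI 89.3%.

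**Dose reductions.** A reduction is "A dose change where the prescribed dose level is lower than the previous prescribed dose level", and for carboplatin the fall must exceed 15%. A later note deals with any drop below the last dose above zero, and says that it "will be counted as a dose reduction even if this decrease has been directly preceded by an interruption: see record 8". Yet the dose-change table (captioned Table 2-8, cited in the text as Table 2-10) marks record 8 No and describes it as a dosing error.

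**Duration term.** The DI formula lines name the duration of the whole study treatment. A later sentence and the worked examples use each component's own duration.

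**The concern.** The SAP presents these examples as instruction on how to compute the quantities, so they will be used as a programming template. Someone who codes the definitions and someone who codes the examples will get different RDI values and different reduction counts from the same records. Dose reductions and dose intensity are named secondary safety endpoints (Protocol Table 2-1, SAP Table 1-1). Reductions are derived programmatically because the eCRF collects only dose changes. ORR and the proof-of-preliminary-efficacy decision do not depend on any of this.

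**Working it through.** **1. LAG525 Example 1**

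Inputs from Table 2-4: first dose 13Jun2018; last non-zero dose 25Jul2018; cut-off 23Aug2018; actual cumulative dose 3 × 400 = 1200 mg. SAP 2.4.1 sets planned DI at 400 mg/cycle.

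Formulas: days = last exposure date − first dose date + 1; cycles = days/21; DI = actual cumulative dose/cycles; RDI = DI/planned DI.

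| | As printed | Under Table 2-3 |
|---|---|---|
| Last exposure date | 23Aug2018 | 25Jul2018 + 20 days = 14Aug2018 |
| Days | 72 | 63 |
| Cycles | 72/21 = 3.43, rounded up to 4 | 63/21 = 3, no rounding |
| DI (mg/cycle) | 1200/4 = 300 | 1200/3 = 400 |
| RDI | 300/400 = 75% | 400/400 = 100% |

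The printed figures reproduce once the cut-off is taken as the end date. But 14Aug2018 falls before 23Aug2018, so Table 2-3 truncates nothing and the round-up is not triggered. Truncation would have applied had the 15Aug2018 dose been given, since 15Aug2018 + 20 days = 04Sep2018. Using the cut-off without rounding gives 1200/(72/21) = 350 mg/cycle, RDI 87.5%, so the later end date and the round-up each account for half of the 25-point gap.

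The planned dose of 1600 mg conflicts with its definition in the same way. Planned dosing up to the last non-zero dose covers three administrations, 1200 mg. This does not add to the RDI error: planned DI is 400 mg/cycle either way (1600/4 or 1200/3).

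For one held cycle after n full doses (n assumed), the Example 1 method gives RDI = n/(n+1): 3/4 = 75%, 6/7 = 86%, 12/13 = 92%. Table 2-3 gives 100% each time.

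**2. Carboplatin Example 2**

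- Printed: 15.8/3 = 5.3 AUC/cycle; 15.8/17.7 = 89.3%.
- From the listed doses: 5.9 + 5.9 + 5 = 16.8; 16.8/3 = 5.6 AUC/cycle; 16.8/17.7 = 94.9%.

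Rounding does not explain 15.8. The lowest values that could round to the listed doses (5.85, 5.85, and 4.5 if the last is rounded to a whole number) sum to 16.2. Carboplatin Example 1 does check: 6 + 6 + 5 = 17, and 17/18 = 94.4%.

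**3. Record 8**

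| Record | Prescribed AUC | Administered AUC | Table verdict |
|---|---|---|---|
| 6 | 5 | 5 | No |
| 7 | 0 | 0 | No (interruption) |
| 8 | 5 | 4 | No (dosing error) |

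The last non-zero prescribed dose before record 8 is 5 (record 6), so the prescribed dose has not fallen and the definition gives no reduction. The administered dose falls from 5 to 4, which is 20%, and the note counts that fall. The table marks two reductions (records 4 and 12); following the note gives three. Two further notes in the same list also count dosing-error decreases as reductions in certain sequences, so the text supports both readings.

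**The case against.** The strongest counter-argument concerns Example 1. Its arithmetic closes, and it gives its reason for using the cut-off. Example 2 and both carboplatin examples attach the 20-day extension to permanent discontinuation. Four examples applying the same distinction suggest that it is deliberate and that Table 2-3 merely omits it. SAP 5.1.1, Scenario 1, also carries ongoing subjects to the cut-off.

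That may well be the intent, but the definitions do not say so. Scenario 1 covers a completely missing dose end date, which is not the case here. As written, the rule and the example give different answers.

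The objection on scope largely stands. Example 1 matters only when a drug is not permanently discontinued at a cut-off and was last given more than 20 days before it. The primary analysis (cut-off 27-Feb-2020) was already done. By protocol amendment 4, 85 of 88 participants had discontinued treatment. SAP 5.1.1 expects every end-of-treatment page to be complete before the final lock.

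The addition error is not disputed, and a correct program would not reproduce it. The record 8 citation may be a stale cross-reference, since table numbers in this section are visibly offset. Even so, the note's wording conflicts with the definition. That conflict is not limited to ongoing participants: it can affect carboplatin recipients at any cut-off, and 34 + 34 = 68 participants were randomized to Arms 2 and 3.

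**Conclusion.** The concern holds; the section is wrong as written and should be corrected. Example 1 shows RDI 75% where Table 2-3 gives 100%. Carboplatin Example 2 shows 89.3% where its own doses give 94.9%. The dose-change example yields two or three reductions depending on which sentence is followed. The duration term in the DI formula lines is a wording slip with clear intent.

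The effect is confined to descriptive exposure summaries. The documents do not show how many participants would be classified differently, and the 86% and 92% figures rest on assumed numbers of prior doses. The finding on Example 1 takes Table 2-3 as the governing rule. If ongoing participants were meant to be handled differently, the definitions need changing instead of the example.

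**What to change.** 1. Choose one end-of-exposure rule and put it in the definitions. Either recompute Example 1 under Table 2-3 (63 days, 3 cycles, 1200 mg planned, RDI 100%), accepting that a trailing held dose in an ongoing participant will not show in RDI. Or, if such doses are meant to count, add that condition to Table 2-3 and to the planned-cumulative-dose definition, and keep Example 1.
2. Correct carboplatin Example 2 to 16.8 AUC, 5.6 AUC/cycle and 94.9%.
3. Remove or correct the record 8 citation, and state whether the dosing-error notes are exceptions to the prescribed-dose definition.
4. In the DI formula lines, name the component's own duration of exposure.

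The cost is SAP wording, corrections to the worked examples, and a check of the exposure and dose-reduction programs against the chosen rules.
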